**Objectives of the Investigation:**

The study will examine whether inhibition of the pre-supplementary motor area (pSMA) using transcranial magnetic stimulation (TMS) normalizes activity in pSMA-connected circuits, improves response inhibition, and reduces compulsions in adolescents with OCD.

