**Study Design:**

We will use a within-subject, counterbalanced design comparing TMS vs Sham in a brief 2-visit protocol enrolling 14 youth (age 13-18) with OCD. At each visit, youth will complete the Stop Signal Task (SST) with concurrent electroencephalogram (EEG) pre- and post- TMS or Sham. TMS will be delivered over pSMA using continuous TBS (cTBS). After each visit, youth will rate symptoms using ecological momentary assessment (EMA).

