**Study Procedures:**

Overall, study procedures include (a) pre-screening for initial eligibility determination; (b) clinical interview for final eligibility determination, (c) two study visits at which youth will receive TMS or Sham and complete EEG and SST procedures. Assessment procedures include structured diagnostic interviews, and safety screening for TMS. Interested participants will complete a brief phone screen and provide medical records for review before scheduling a clinical interview. Clinical Interview: Participants will complete informed consent (signature required from one parent/guardian), child assent, and assessment of inclusion/exclusion criteria (Mini Kid, CYBOCS, TMS screen; see Measures). Interviews will be administered by the RA, who is already employed at PARC and trained to a reliable standard on all measures. At each of visits 1 and 2, participants will complete a TMS safety screen and medication tracking form; they will then complete the SST with concurrent EEG pre- and post- TMS or Sham. The AEQ will be completed at the end of each visit. Between visits, youth will rate symptoms using EMA (see Measures). Visits 1 and 2 will occur at least one week apart to ensure that any acute TMS effects are no longer active by visit 2. Single session rTMS aftereffects on EEG suggests aftereffect durations <70 min.

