#### Study Design Flow Chart:

#### Study Assessment Measures:

- 1) Mini-Kid; the Mini-Kid 7.0 is a brief, structured interview measuring psychiatric diagnoses in children according to DSM-V and ICD-10 criteria.
- 2) CY-BOCS, is the “gold standard” clinical interview for assessment of OCD symptoms.
- 3) Screening Questionnaire for TMS Candidates; screens for TMS contraindications and will be administered in an interview format with both the child and parent present.
- 4) TMS Adverse Effects Questionnaire (AEQ) is a 13-item questionnaire completed by patient (items 1-10) and clinician (items 11-13).
- 5) The SST is a well-validated computerized task measuring RI. The SST is a visual choice reaction time task in which participants watch arrows (left or right) on the screen and respond by pressing the appropriate button. In a randomly assigned proportion of trials, an audible signal is heard after presentation of the arrow, and subjects are instructed to inhibit the motor response (button press). The inter-stimulus interval and stop-signal delay are varied according to individual performance so that each person can successfully inhibit responses to 50% of stop trials. SSRT (time required to inhibit a prepotent motor response) is calculated from these data. Successful stop trials (i.e., those in which a motor response is successfully inhibited) are most relevant for understanding functional neural correlates of RI, and will be of primary interest in EEG analyses (see below).
- 6) EMA will be used to obtain youth ratings on three items (modified from NIMH rating scales) assessing obsessions, compulsions, and mood on a 7-point scale (1 = not at all to 7 = very much). These items have shown differential change with frequent assessment post-TMS for adults with OCD and have been used in EMA studies of OCD. Youth will receive a text message prompt every two hours (between 9am and 9pm) over the two days following the clinical interview and each study visit (6 days total). The text prompt will include a redcap link for completing EMA items. Similar EMA items and procedures have been used successfully with adolescents of diverse backgrounds in a large number of studies to date.

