#### Description of the Statistical Methods:

Statistical methods align with the Aims of the study, which are as follows:

**Aim 1. Safety and Tolerability.** TMS will be safe and tolerable, as indicated by a comparable rate of side effects associated with TMS vs. Sham (hypothesis 1) and no serious adverse events associated with TMS (hypothesis 2).

**Aim 2. Neural Target Engagement: TMS-induced changes in the RI Network.** Compared with sham, participants will demonstrate significant post-TMS neural changes during SST stop trials, as indicated by increase in frontocentral P3 amplitude

**Aim 3. Behavioral Target Engagement: TMS-induced changes in RI behavior.** Compared with sham, participants will demonstrate a significant post-TMS decrease in SSRT (Hypothesis 1) and EMA-rated compulsions (Hypothesis 2).

**Data Analysis.** We will test **Aim 1 (Safety and Tolerability)** using descriptive data as follows. Hypothesis 1. TMS will be safe and tolerable as shown by total AEQ ratings that are no more than 1 SD higher for TMS vs. Sham (hypothesis 1) and no serious adverse events associated with TMS reported on the AEQ (hypothesis 2). Remaining analyses will use Generalized Linear Mixed Models (GLMM), a variant of Generalized Linear Models (GLM; of which ANOVA, t-test, and regression are special cases) that permit outcome variables with distributions other than Gaussian and additionally permit modeling both fixed and random hierarchical (nested) effects. For each model, the distribution will be selected based on theory (e.g., Poisson for count) and model residuals. **Aim 2 (Neural Target Engagement).** We will examine the significance of TMS-induced neural changes during SST stop trials by testing an interaction between visit type (TMS vs. Sham) and timing of assessment (pre vs. post TMS/Sham) for the the outcome of frontocentral P3 (hypothesis 1). **Aim 3. Behavioral Target Engagement:** We will test an interaction between visit type (TMS vs. Sham) and timing of assessment (pre vs. post TMS/Sham) on RI efficiency as measured by the SSRT (hypothesis 1) and EMA-rated compulsions (hypothesis 2).

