**Sample size and power.** We anticipate some minimal EEG/SST data loss and participant attrition, very conservatively resulting in a final sample size of  $N = 10$  participants (each with four EEG/SST observations; pre- and post- TMS and Sham). Given this sample size and assuming .80 correlation among repeated measures, power calculations indicate that **Aim 2 and 3** analyses would reach 0.8 power with a medium effect size (Cohen's  $d = 0.51$ ) and alpha = .05. Assuming .60 correlation among repeated measures, analyses would reach .8 power with a medium-large effect size ( $d = .70$ ). Using a TMS protocol similar to that proposed in this application, Obseso (2017) found large effect sizes for cTBS of pSMA on SSRT in healthy adults ( $d = .95$ ). Available data for proposed outcome variables suggest that repeated measures correlations will fall between .60 and .80, with SSRT showing correlations between .65-.73 and P3 showing correlations of .68-.71.

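### The four-cell TMS/Sham by pre/post interaction does not fit EMA compulsions, which have three rating blocks and no separate pre block for visit 2

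*Combined protocol and SAP*

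**What the plan says.** The Objectives ask whether stimulation "improves response inhibition, and reduces compulsions in adolescents with OCD". Aim 3 turns this into two hypotheses: "participants will demonstrate a significant post-TMS decrease in SSRT (Hypothesis 1) and EMA-rated compulsions (Hypothesis 2"). The Data Analysis paragraph tests both with one model term, an interaction of visit type with "timing of assessment (pre vs. post TMS/Sham) on RI efficiency as measured by the SSRT (hypothesis 1) and EMA-rated compulsions (hypothesis 2").

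The EMA schedule is in item 6 of Study Assessment Measures. Prompts are sent "over the two days following the clinical interview and each study visit (6 days total"). Study Design and Study Procedures agree: "After each visit, youth will rate symptoms using ecological momentary assessment (EMA") and "Between visits, youth will rate symptoms using EMA (see Measures"). No section names an EMA block as the pre value for visit 2.

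The Sample size and power paragraph gives one statement for Aims 2 and 3. It describes participants as "each with four EEG/SST observations; pre- and post- TMS and Sham", and adds: "Available data for proposed outcome variables suggest that repeated measures correlations will fall between .60 and .80". The supporting figures it then cites are for SSRT and P3 only.

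**The concern.** A visit type by timing interaction needs a pre and a post value under each condition. The SST and EEG supply these because they are run before and after stimulation at both visits. EMA does not: it has one block before any stimulation and one after each visit. The block after visit 1 is already that visit's post value, and it is the only EMA before visit 2. Someone has to decide what goes in the empty cell, and the plan does not say what.

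This is the plan's only test of a symptom outcome. With 10 to 14 participants, the choice can change the estimate, the error rate or the power.

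**Working it through.** **Inputs.** Three EMA blocks of two days (Study Assessment Measures, item 6). Four SST/EEG values per participant, N = 10 analysed, correlations 0.60 to 0.80 (Sample size and power). N = 14 enrolled (Participants).

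**Assumptions.** One mean per block: B (interview), T (post-TMS), S (post-Sham). Independent residuals with SD 1 around each participant's level, an even split of orders, an effect τ in T only, two-sided 0.05. The plan gives no EMA correlation; its 0.60 to 0.80 is borrowed where one is needed.

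**The plan's power figure.** The method is not stated. A repeated-measures F test with four measurements comes close: f = d/2, λ = f² × N × 4/(1 − ρ), df 3 and 27.
- d = 0.51, ρ = 0.80: λ = 0.255² × 40/0.20 = 13.0, power 0.81.
- d = 0.70, ρ = 0.60: λ = 0.35² × 40/0.40 = 12.25, power 0.79.

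With three measurements the same formula gives 0.73 and 0.70. The stated 0.8 therefore depends on four values per person, which EMA does not have.

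**Count.** 6 days / 2 days = 3 EMA blocks, against 2 × 2 = 4 cells.

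**Direct contrast, T − S.** Variance 2, SE = √(2/N) = 0.378 (N = 14) and 0.447 (N = 10). The interview mean is constant within a participant, so with complete data entering it as a covariate leaves this SE unchanged. With a visit-number term (df N − 2), 80% power needs τ = 1.154 and 1.431 residual SDs. Multiplying by √(1 − ρ) gives total-SD units. At N = 10, d = 1.431 × √0.20 = 0.64 (ρ = 0.80) and 1.431 × √0.40 = 0.91 (ρ = 0.60). Power figures below are at these values of τ.

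**Preceding block as pre.**
- TMS first: (T − B) − (S − T) = 2T − B − S, expectation 2τ.
- Sham first: (T − S) − (S − B) = T + B − 2S, expectation τ.
- The average is 1.5τ, and zero when τ is zero. Variance is 4 + 1 + 1 = 6, so the true SE is √(6/14) = 0.655 at N = 14.
- A four-row fit with a participant intercept pools the three within-person contrasts (interaction, visit type, timing): residual variance (6 + 2 + 2)/(4 × 3) = 0.833, model SE √(4 × 0.833/14) = 0.488. That is too small. Simulated type I error is 0.142-0.144 at both N.
- Tested instead as one contrast per participant, type I error is 0.05 and power 68%.

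**Interview block copied into both pre cells.**
- (T − B) − (S − B) = T − S, so the estimate is right.
- The four-row fit pools variances 2, 2 and 6 to the same 0.833 and reports 0.488 where the true SE is 0.378.
- Simulated type I error is 0.015 (N = 14) and 0.017 (N = 10), with power 67% and 70%.

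**Interview block for the first session only.**
- Each participant fills three of four cells. The interaction is estimable only by comparing T − B in one order with S − B in the other.
- Variance is 2/(N/2) + 2/(N/2) = 8/N, so SE = 0.756 (N = 14) and 0.894 (N = 10), twice the direct value. With random participant effects at ρ 0.6 to 0.8 it is 0.732-0.745 and 0.866-0.882.
- Power is 31-33% (N = 14) and 33-34% (N = 10).

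**Prompt-level fitting.** Two-hourly prompts from 9am to 9pm give about 7 a day, 14 a block. Simulated type I error at N = 14 with a participant effect only, by assumed share of within-person variance lying between blocks:

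| Share | Direct contrast | Preceding block | Copied baseline |
|---|---|---|---|
| 0 | 0.05 | 0.12 | 0.004 |
| 0.1 | 0.20 | 0.29 | 0.076 |
| 0.3 | 0.39 | 0.50 | 0.24 |

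Here omitting a participant-by-visit effect matters as much as the pre coding, and it makes even the direct contrast too liberal.

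**The case against.** The best defence is that this is an unstated coding rule more than a wrong analysis. One block precedes all stimulation, so the interview block as common pre is the natural reading. Its estimate is exactly post-TMS minus post-Sham, and the planned mixed-model framework can fit a shared baseline. No section states either of the other two codings. All of that stands. It does not rescue the test as written: four rows with a duplicated baseline still misstate the standard error, and the text specifies the four-cell interaction. The flow chart is not visible in the text available. It might label the baseline block, but it cannot change the six-day count.

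Three stronger readings are tempting and not supported.
- A reader might infer that the EMA test will run at 14%. That needs one particular coding, a four-row fit and one mean per block; the plan commits to none of these.
- A reader might set the EMA detectable effects of 0.64 to 0.91 beside the stated 0.51 to 0.70 and conclude that EMA is the less sensitive test. The two are not like for like. On the same basis at N = 10, a one-degree-of-freedom four-cell interaction has variance 4 instead of 2 and needs d = 0.64 × √2 = 0.91 to 0.905 × √2 = 1.28. The direct EMA contrast is the more sensitive of the two.
- A reader might infer that hypothesis 2 cannot be tested without more data. It can, from the two post-visit blocks.

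**Conclusion.** The concern holds as a mismatch between the stated test and the EMA schedule, and that mismatch rests on the documents alone. Each way of filling or dropping the fourth cell that was checked gives an inflated estimate, a wrong standard error or a much larger one. The sizes are conditional on one mean per block, equal residual variance, an even split, an effect confined to the post-TMS block and, where a correlation enters, values the plan supports only for SSRT and P3. They should not be quoted for prompt-level models. The power paragraph does not describe the EMA test. Whether its figures are right for SSRT and P3 is a separate question, which this point does not settle. It is worth correcting before any EMA data are analysed.

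**What to change.** 1. In the Data Analysis paragraph, replace the interaction for EMA compulsions with a within-person post-TMS versus post-Sham contrast. Outcomes: the two post-visit blocks. Fixed effects: visit type and visit number. Covariate: the interview-block mean, entered once. Random effects: participant, plus participant-by-visit if individual prompts are modelled. State whether means or prompts are analysed. Keep the interaction for SSRT and P3.
2. In Sample size and power, say that the figures rest on four EEG/SST observations and on SSRT and P3 correlations, and so do not cover EMA. Optionally add the EMA detectable effect (direct contrast, 80% power, one mean per block, N = 10): d about 0.64 at an assumed correlation of 0.80 and 0.91 at 0.60. Do not compare it with the stated 0.51 to 0.70.

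The cost is wording only, with no new data collection. The one downside is that the EMA test no longer has the same form as the SSRT and P3 tests.

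### The 0.8 power statement covers EMA-rated compulsions, but its inputs (four pre/post observations, SSRT and P3 correlations) do not apply to that outcome

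*Combined protocol and SAP*

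**What the plan says.** The sample size and power paragraph (under Description of the Statistical Methods) allows for data loss and attrition, "very conservatively resulting in a final sample size of" N = 10 out of 14 enrolled, "each with four EEG/SST observations; pre- and post- TMS and Sham". On that basis, and "assuming .80 correlation among repeated measures", it says of Aims 2 and 3 together that "analyses would reach 0.8 power with a medium effect size", d = 0.51, at alpha .05. It adds: "Assuming .60 correlation among repeated measures, analyses would reach .8 power with a medium-large effect size", d = .70. The correlations are supported by published values, "SSRT showing correlations between .65-.73" and P3 showing .68 to .71. No value is given for EMA.

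The Data Analysis paragraph tests Aim 3 as a visit type by timing (pre versus post) interaction "on RI efficiency as measured by the SSRT (hypothesis 1) and EMA-rated compulsions (hypothesis 2". EMA compulsions are thus inside the aims for which power is claimed, with the same planned test as SSRT.

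Study Assessment Measures, item 6, schedules EMA prompts every two hours from 9am to 9pm "over the two days following the clinical interview and each study visit (6 days total". The Study Design section likewise places EMA after each visit.

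**The concern.** The power figure is tied to four readings per person: before and after stimulation, at each of two visits. SSRT and P3 have those readings. EMA compulsions have three windows, none of them placed just before a visit as that visit's own baseline. The correlation assumption is also drawn from other outcomes.

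The consequence is for interpretation. Reducing compulsions is one of the trial's stated objectives, and EMA-rated compulsions is the only symptom measure that carries a hypothesis. If the result is null, a reader could set it against a claim of 80% power at a medium effect that was not calculated for this outcome.

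**Working it through.** **Inputs.** From the plan: N = 10 analysed, 14 enrolled; four EEG/SST observations per person; correlations .80 and .60; d = 0.51 and .70; alpha .05, sidedness not stated; three two-day EMA windows with 6 or 7 prompts a day, so 12 to 14 per window. Assumed here because the plan does not say: two-sided tests, equal variances and a common correlation ρ. Applying ρ = .80/.60 to EMA is also an assumption.

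**1. Reproducing the plan's figure.** The plan names no method. A one-group within-subject F-test with m measures uses f = d/2, λ = f²·N·m/(1 − ρ), and df = m − 1 and (N − 1)(m − 1). With N = 10 and m = 4 (df 3 and 27):

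- ρ = .80, d = 0.51: λ = 0.255² × 40 / 0.20 = 13.0; power 0.813.
- ρ = .60, d = .70: λ = 0.35² × 40 / 0.40 = 12.25; power 0.787.

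Both are close to 0.8. A one-sided normal approximation on two observations also fits (0.817 and 0.797), but it does not use the four observations the text names.

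**2. What the EMA schedule supplies.** Let B be the post-interview window, T the post-TMS window and S the post-Sham window. With B as the only baseline, the visit type by timing contrast is (T − B) − (S − B) = T − S. The baseline cancels, leaving a two-window comparison.

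**3. The plan's apparent method with fewer measures, N = 10, ρ = .80/.60.**

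| Measures | Detectable d at 0.8 power | Power at d = 0.51/.70 |
|---|---|---|
| 4 (EEG/SST) | 0.50 / 0.71 | 0.81 / 0.79 |
| 3 (all EMA windows) | 0.55 / 0.78 | 0.73 / 0.70 |
| 2 (post-TMS, post-Sham) | 0.63 / 0.89 | 0.62 / 0.60 |

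The two-measure row equals a two-sided paired t-test on T − S, with d = dz·√(2(1 − ρ)). At N = 10, dz = 0.996, giving 0.996 × √0.4 = 0.63 and 0.996 × √0.8 = 0.89. At N = 14, dz = 0.810, giving 0.51 and 0.72.

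**4. Sensitivity to what is unstated.** If the EMA correlation were .40 (assumed), the two-window detectable d at N = 10 would be 1.09. If prompt-level data are modelled, let the total prompt variance be 1, v the person-by-window variance, e the momentary variance and k the prompts answered. The detectable difference is then 0.996·√(2(v + e/k)). With v = .05, e = .45, k = 14 it is 0.40 prompt-level SD; with v = .30, e = .40, k = 8 it is 0.83. These variance splits are assumptions, and their unit is not the window-mean SD used in step 3.

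**5. The planned test for SSRT and P3.** The interaction has 1 df. Read as a difference of differences in raw SD units, its variance per person is 4(1 − ρ) and λ = N·d²/(4(1 − ρ)):

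- ρ = .80: 10 × 0.51² / 0.8 = 3.25; power 0.36.
- ρ = .60: 10 × 0.70² / 1.6 = 3.06; power 0.35.

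The detectable effects are 0.89 and 1.26 SD.

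**The case against.** The case against a larger claim is strong, and most of it stands.

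- **The arithmetic is not wrong.** The stated figures reproduce, and the text labels the observations as EEG/SST. The fault is in the scope of the sentence.
- **EMA power need not be lower.** A reader might infer that EMA has about 60% power where 80% is claimed. The documents do not support that. The 62%/60% figures set a 1-df paired comparison beside a 3-df omnibus test; with three windows in the same F-test, power is 0.73/0.70. The plan also specifies mixed models with nested random effects, and 12 to 14 prompts per window could help or not, depending on variances it does not give.
- **N = 10 is partly an EEG/SST allowance.** Losing EEG data does not remove EMA ratings. At N = 14 the illustrative detectable effects, 0.51 and 0.72, almost equal the stated ones. EMA non-response could pull the other way and is not addressed.
- **The post-visit-1 window might serve as the pre-value for visit 2.** The documents do not say so, and one set of ratings would then be both a post and a pre value. The contrast would also depend on order: 2T − S − B if TMS comes first, T − 2S + B if Sham comes first.

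None of this supplies a basis for the stated power on EMA. It shows that the power is unknown, not that it is known to be low.

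**Conclusion.** The point holds as one of scope: the 0.8 power claim at d = 0.51 or .70 has no basis for Aim 3 Hypothesis 2. This rests on the EMA schedule and on the absence of any EMA correlation, and needs no outside figure. The size of any shortfall is undetermined. The illustrative 0.63/0.89 SD at N = 10 and 0.51/0.72 SD at N = 14 depend on one mean per window, a two-sided paired t-test, and correlations borrowed from SSRT and P3.

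A reader might also infer that the 0.8 figure is sound for P3 and SSRT once EMA is removed. That does not follow. The figure matches a 3-df omnibus test, whereas the plan tests a 1-df interaction, whose power in raw SD units is about 0.36/0.35 at the stated effects. That reading of d is itself an assumption, since the plan does not define d for the interaction, so the matter needs its own check.

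**What to change.** Change the power paragraph as follows:

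- Remove EMA compulsions from the 0.8 power sentence.
- State the EMA contrast the schedule supports: post-TMS versus post-Sham, with the post-interview window as a shared baseline not tied to either visit. Align the Aim 3 Hypothesis 2 analysis text with it.
- Report the EMA result as an estimated difference with a confidence interval.
- If a detectable EMA difference is given, state it with its assumptions (summary per window, test, correlation, N, response rate). The figures above can serve as a conditional example, not as a design claim.
- Recheck the P3 and SSRT power separately against the 1-df interaction, and state the method, the sidedness and the definition of d.

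The EMA change costs a few sentences and alters no visit, procedure or sample size. The downside is that the power statement covers fewer outcomes and looks less favourable.

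### The 0.8 power stated for 10 completers does not match the planned visit type by timing interaction, and the size and direction of the gap depend on an undefined d

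*Combined protocol and SAP*

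**What the plan says.** Study Design has each participant tested before and after stimulation at both visits: "youth will complete the Stop Signal Task (SST) with concurrent electroencephalogram (EEG) pre- and post- TMS or Sham". Under Description of the Statistical Methods, the Data Analysis text has P3 (Aim 2) analysed in a generalized linear mixed model by "testing an interaction between visit type (TMS vs. Sham) and timing of assessment (pre vs. post TMS/Sham"). It plans the same interaction for SSRT and for EMA-rated compulsions (Aim 3).

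The Sample size and power paragraph expects 10 of the 14 enrolled to be analysable, "each with four EEG/SST observations; pre- and post- TMS and Sham". For a correlation of .80 among repeated measures and alpha .05 it says that "analyses would reach 0.8 power with a medium effect size" (d = 0.51). For .60 it says: "Assuming .60 correlation among repeated measures, analyses would reach .8 power with a medium-large effect size" (d = .70). In support it states that "repeated measures correlations will fall between .60 and .80, with SSRT showing correlations between .65-.73" and "P3 showing correlations of .68-.71". For comparison it cites a study that "found large effect sizes for cTBS of pSMA on SSRT in healthy adults" (d = .95).

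**The concern.** In a 2 x 2 within-subject design the planned interaction is one contrast: the pre-post change at the TMS visit minus the pre-post change at the Sham visit. Its power at a given d depends heavily on whether d is that net change over the SD of one measurement, an effect scaled on change scores, or a transformed f. The plan gives no contrast, no SD, no sidedness and no degrees of freedom, and it does not name the test behind the calculation.

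This paragraph is the plan's only justification of the sample size. As it stands, a reader cannot tell whether 10 completers give roughly a 35%, 60% or 90% chance of detecting the stated effect. The labels medium and medium-large, and the comparison with d = .95, cannot be checked either. The statement also covers all of Aim 3, although its calculation rests on four EEG/SST observations. EMA-rated compulsions come from prompts over two days after the clinical interview and after each visit (six days in all; Study Assessment Measures, item 6).

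**Working it through.** **Inputs** (Sample size and power): N = 10; four measurements per person; alpha .05; pairs (d .51, rho .80) and (d .70, rho .60). The test comes from Data Analysis. Assumed here: Gaussian outcome, complete data, no period effect, and a single-measurement SD of 1. Results are given as first pair / second pair. Error df run from 9 (subject level, N - 1) to 27 (pooled, 3(N - 1)), because the plan does not fix them.

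**Step 1. Recovering the plan's 0.80.** Two unstated calculations come close.
- A 3-df omnibus F over four measurements, with f = d/2 and lambda = 4N(d/2)²/(1 - rho). For the first pair, 40 × 0.255²/0.20 = 13.0; for the second, 40 × 0.35²/0.40 = 12.25. Power on (3, 27) df is 0.813 / 0.787.
- A one-sided normal-approximation paired comparison, with ncp = √N·d/√(2(1 - rho)) = 2.55 / 2.47. Power is 0.817 / 0.797. With t on 27 df it is 0.800 / 0.779.

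**Step 2. Power of the planned 1-df interaction, N = 10.** Let D be the TMS change minus the Sham change. With a common rho, each change has variance 2(1 - rho) and the two changes have covariance rho - rho - rho + rho = 0. So Var(D) = 4(1 - rho).

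- (a) d = D over the SD of one measurement: ncp = √N·d/(2√(1 - rho)) = 1.80 / 1.75.
- (b) d in change-score SDs, with rho the correlation between the two change scores: ncp = √N·d/√(2(1 - rho)) = 2.55 / 2.47.
- (c) f = d/2 wholly on the interaction: ncp = √N·d/√(1 - rho) = 3.61 / 3.50. This implies a net change of 2d, that is 1.02 / 1.40 SD.

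| Reading | Two-sided, 9 df | Two-sided, 27 df |
|---|---|---|
| (a) | 0.364 / 0.347 | 0.413 / 0.393 |
| (b) | 0.623 / 0.598 | 0.69 / 0.67 |
| (c) | 0.893 / 0.875 | 0.935 / 0.921 |

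One-sided, over the same df, (a) gives 0.49-0.55 and (c) at least 0.94. Neither equals 0.80.

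**Step 3. Effect needed for 0.8 power, two-sided, N = 10** (rho .80; rho .60).
- (a) 0.82-0.89; 1.16-1.26.
- (b) 0.63; 0.89 (9 df), in change-score SDs.
- (c) 0.41-0.45; 0.58-0.63.

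Readings (a) and (c) are the same test on two scales: doubling d in (c) gives the net change in (a), apart from rounding.

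**Step 4. The cited d = .95.** If it were on scale (a), two-sided power would be 0.85-0.90 at rho .80 but 0.56-0.63 at rho .60. Its contrast and SD are not given, so it cannot be placed on any of these scales.

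**The case against.** The strongest reply is that the figures are sound for a one-sided test. The hypotheses are directional (P3 increases, SSRT decreases), sidedness is not stated, and a one-sided paired comparison returns about 0.80 at both pairs, at least as closely as the omnibus F. It is also a 1-df comparison, so it could describe the interaction. What stands is that undeclared sidedness is as plausible a source as a 3-df test, and which was used is inference. But the one-sided route fits the interaction only if rho is the correlation between change scores. The plan describes rho as the correlation among repeated measures and supports it with values for SSRT and P3 themselves. Under a common rho of that kind the two change scores are uncorrelated (Step 2), and the interaction misses 0.80 one-sided as well.

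A second reply is that a common rho is only an assumption. That is true. If all cross-visit correlations are equal, only the same-visit pre-post correlation matters, and it may exceed the cited values. For reading (a) to reach 0.8 at N = 10 it would have to be 0.92-0.93 (d .51) or 0.86-0.88 (d .70). The plan does not report it, and it expects correlations between .60 and .80.

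Third, the three readings are not exhaustive, and the model's df method is unspecified. This widens the ambiguity rather than removing it.

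A reader might also infer that the trial is underpowered, that the sponsor certainly powered the wrong test, or that a non-significant interaction would be uninterpretable. The documents support none of these. Reading (c) exceeds 0.80, the source of the stated figure is unknown, and a completed result is read from its estimate and confidence interval.

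**Conclusion.** The concern holds as a mismatch between the power statement and the planned test, not as a slip in arithmetic: 0.80 can be recovered, but not for the interaction with rho as the plan describes it. At the stated pairs, two-sided power with 10 completers falls well short of 0.80 on one definition of d and above it on another, so the direction of the error depends on the missing definition.

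The firmer result is the detectable effect in Step 3, reading (a). It does not depend on which d the authors meant, only on a two-sided .05 test, a common correlation and complete data from 10 participants. A net change of that size is not well described as medium. These figures concern P3 and SSRT only.

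**What to change.** Revise the Sample size and power paragraph. Name the visit type by timing interaction on P3 and SSRT as the powered test, define d (contrast and SD), state sidedness and df, and replace the 0.8 claim with figures for that contrast. For example:

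*The powered test is the 1-df visit type by timing interaction on P3 and on SSRT. With 10 completers, two-sided alpha .05 and a common correlation among the four measurements, 0.8 power requires a TMS-Sham difference in pre-post change of 0.82-0.89 single-measurement SD at correlation .80 and 1.16-1.26 SD at correlation .60 (27 to 9 df). These figures do not cover EMA-rated compulsions.*

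If another scale or a one-sided test was intended, state it and give the matching figure. If change scores were meant, say that rho is the correlation between them and justify its value. Drop the labels medium and medium-large for this contrast, and give the contrast and SD of the cited d = .95 before comparing it.

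The cost is one reworded paragraph. The stated detectable effect may look less favourable; sample size, design and analysis do not change.
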